7. APPENDICES

7.1. Questionnaire/Scoring

In questionnaires, if multiple responses are provided to a single-response question, the question is deemed as missing.

7.1.1. Neuropathy Impairment Score (NIS)

NIS total score is the sum of NIS-W, NIS-R, and NIS-S, these are described in detail below.

Assessment Tool	Maximum Total Points	Components (maximum points)
NIS	244	
 • NIS-W: Weakness (192) • NIS-R: Reflexes (20) • NIS-S: Sensation (32)

- NIS-W is the sum of the cranial nerve components (3rd nerve, 6th nerve, facial weakness, palate weakness, tongue weakness) and muscle weakness components (respiratory, neck flexion, shoulder abduction, elbow flexion, brachioradialis, elbow extension, wrist flexion, wrist extension, finger flexion, finger spread, thumb abduction, hip flexion, hip extension, knee flexion, knee extension, ankle dorsiflexors, ankle plantar flexors, toe extensors, toe flexors). Assessments are performed separately for the right- and left-hand side of the body. Scoring for each component is 0 (normal), 1 (25% weak), 2 (50% weak), 3 (75% weak), 3.25 (move against gravity), 3.5 (movement, gravity eliminated), 3.75 (muscle flicker, no movement), and 4 (paralysis). The maximum total score for NIS-W is 192.
- NIS-R is the sum of the reflex components (biceps brachii, triceps brachii, brachioradialis, quadriceps femoris, and triceps surae). Assessments are performed separately for the right and left foot. Scoring for each component is 0 (normal), 1 (decreased) and 2 (absent). Adjustments are made for the age of the patient (eg, absent reflexes in a patient older than 60 is assessed as 0, or normal). The maximum total score for NIS-R is 20.
- NIS-S is the sum of the finger and toe sensation components (TP, pin-prick, vibration, joint position). Assessments are performed separately for the right- and left-hand side of the body. Scoring for the sensory assessment is 0 (normal), 1 (decreased) and 2 (absent). The maximum total score for NIS-S is 32.

Missing values will not be imputed. If a component score (NIS-W, NIS-R or NIS-S) is missing, then the NIS total score is considered as missing.

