6.1. Screening and Baseline Assessments

An informed consent form (ICF) that has been approved by the appropriate Institutional Review Board (IRB)/Independent Ethics Committee (IEC) must be signed by the patient before the Screening procedures are initiated. All patients will be given a copy of the signed and dated ICF.

Patients will be screened to ensure that they meet all the inclusion criteria and none of the exclusion criteria. Patient demographic data and medical history/disease history will be obtained. Any changes to medical history occurring between the screening assessment and Day 1 will be updated before study drug administration. An interval medical history will be collected at the Screening and Baseline visit. Only changes since the Screening visit will be collected. Medical history will capture transplant history and evidence for disease progression.

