4.2.1. Demographics and Baseline Characteristics

Age, height, weight, and body mass index (BMI) will be summarized using descriptive statistics. Sex, race, ethnicity, and country will be summarized using counts and percentages.

All demographic and baseline characteristic data will be included in by-patient data listings.

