4.4.2. Secondary Endpoints

4.4.2.1. NIS

Neurologic impairment will be assessed by NIS. The total NIS score is the sum of NIS-W, NIS-R, and NIS-S. Scoring algorithms for NIS score are included in Section 7.1.1. LOCF will be used for imputation for the missing NIS assessments at Month 12 as described in Section 3.10.1.

NIS absolute values and changes from baseline in the composite (total NIS score) and component scores (NIS-W, NIS-R, NIS-S) will be summarized by visit.

Observed NIS scores will be included in a by-patient listing.

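### Does the one-example age rule for reflex scoring in SAP 7.1.1 leave the NIS secondary endpoint undefined?

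*SAP*

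**What the plan says.** SAP 4.4.2.1 states: "Scoring algorithms for NIS score are included in Section 7.1.1". It plans this output: "NIS absolute values and changes from baseline in the composite (total NIS score) and component scores (NIS-W, NIS-R, NIS-S) will be summarized by visit".

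SAP 7.1.1 lists five reflexes for NIS-R: biceps brachii, triceps brachii, brachioradialis, quadriceps femoris and triceps surae. On laterality it says: "Assessments are performed separately for the right and left foot". On grading: "Scoring for each component is 0 (normal), 1 (decreased) and 2 (absent". On age: "Adjustments are made for the age of the patient (eg, absent reflexes in a patient older than 60 is assessed as 0, or normal". On the ceiling: "The maximum total score for NIS-R is 20".

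Protocol 6.2.2 has a neurologist do the testing, says the score comes from findings on physical examination, and does not mention age. Protocol 6.2 leaves further details of performing efficacy assessments to the Study Reference Manual, which is not among the documents. SAP 3.2 makes every non-primary summary descriptive.

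**The concern.** A section named as the scoring algorithm should let two programmers reach the same score, and one example does not do that. Four things are not stated:

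- which of the five reflex pairs are covered;
- what a decreased reflex scores above the cut-off;
- whether the examiner or the analysis program applies the adjustment;
- the date at which age is taken.

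The laterality wording also looks wrong, since three of the five reflexes are in the arm.

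NIS is the neuropathy secondary endpoint. NIS-R change is reported alone and within the total, and there is no control arm against which an artefact would cancel. The inclusion criteria (Protocol 4.1) set a lower age limit of 18 and no upper one, so patients over 60 can enter. If age were re-evaluated at each visit, a patient passing the cut-off on study could lose points for reflexes that had not changed, and that would read as improvement.

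**Working it through.** **1. The plan's own figures (SAP 7.1.1).**
- NIS-R: 5 reflexes × 2 sides × 2 points = 20, as stated.
- NIS-W: (5 cranial nerve + 19 muscle components) × 2 sides × 4 points = 192, as stated.
- NIS-S: 4 modalities × 2 sites (finger, toe) × 2 sides × 2 points = 32, as stated.
- Total: 192 + 20 + 32 = 244, as stated. NIS-R is 20/244 = 8.2% of the scale.

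The ceiling of 20 requires ten reflexes, so the reference to the foot is a clerical slip. The five named reflexes and the maximum settle the count.

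**2. Decreased reflex above the cut-off.** Suppose all five pairs were covered and only the absent grade were reset. Ten absent reflexes would then score 0 and ten decreased reflexes 10 × 1 = 10, so the worse finding would score better. The sensible reading is that decreased also scores 0 wherever absent does.

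**3. Covered reflexes.** With k of five pairs covered and both grades set to 0, NIS-R in a patient over 60 can reach 20 − (2k reflexes × 2 points) = 20 − 4k.

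| k | 1 | 2 | 3 | 4 | 5 |
|---|---|---|---|---|---|
| attainable NIS-R | 16 | 12 | 8 | 4 | 0 |

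This is a range of attainable scores, not an error in a result. If the same mapping is used at baseline and follow-up, an unchanged reflex contributes a change of 0 whatever k is. Coverage affects how much real reflex change is seen. The case k = 5 would fix NIS-R at 0 for everyone over 60, which sits badly with a planned summary of NIS-R change.

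**4. Age date.** If a program applies the rule, baseline age is the natural choice. Protocol 6.1 says of screening: "Patient demographic data and medical history/disease history will be obtained". SAP 4.2.1 treats age as a baseline characteristic: "Age, height, weight, and body mass index (BMI) will be summarized using descriptive statistics". With age fixed, the crossing effect is 0. If age were re-evaluated at each visit, the exposed patients would be those who pass the cut-off before their Month 12 assessment.
- Scheduled Month 12, Weeks 54 to 56: 54 × 7 = 378 days, 378/365.25 = 1.03 years; 56 × 7 = 392 days, 392/365.25 = 1.07 years.
- SAP 3.11 lets an assessment within 3 months stand in when the scheduled one is not performed. Three months is 3 × 30.4375 = 91 days, so (392 + 91)/365.25 = 1.32 years.

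Each unchanged covered absent reflex would drop by 2 points. For one such patient:

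| absent reflexes rescored | fall in score | shift in mean, n = 20 | shift in mean, n = 16 |
|---|---|---|---|
| 1 | 2 | 2/20 = 0.10 | 2/16 = 0.125 |
| 2 (one pair) | 4 | 4/20 = 0.20 | 4/16 = 0.25 |
| 10 (all) | 20 | 20/20 = 1.00 | 20/16 = 1.25 |

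The last row needs all five pairs to be covered and absent. The documents give no ages, so the number of such patients is unknown and may be 0.

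**The case for a change.** The best case for a change is that the same appendix is exact elsewhere. It gives rounding and 50% rules for Norfolk QoL-DN, a 90% item rule for R-ODS, and question-level rules for COMPASS-31. By that standard an example is not an algorithm. The coverage question also arises for every patient over 60, not only for those who pass the cut-off on study. A few lines of text would close it.

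What stands is that the detail is absent from both documents and that SAP 7.1.1 does not point to the manual where it may be. What does not stand is the step from there to a flaw in the analysis. SAP 7.1.1 speaks of how a reflex is assessed, which most naturally describes the neurologist's grading. The program would then only add the entered grades, and coverage and age would belong to the examination instructions. The documents do not settle this, so a gap in the analysis is possible but not established.

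Nor is the obvious remedy clearly a matter of wording. If examiners already grade for age on the day, fixing age at baseline would need unadjusted grades, and the documents do not show that these are recorded.

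**Conclusion.** No change follows. SAP 7.1.1 is thinner than its billing on three points: covered reflexes, who applies the adjustment, and the age date. The decreased-reflex score has one sensible answer, and the laterality wording is clerical. The missing detail concerns an examiner-scored instrument whose conduct is left to study manuals, and analysts can fill it sensibly: sum the grades as entered, or, if the program adjusts, use one age per patient with absent never scoring below decreased.

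Under one consistent mapping, no false change arises. The only route to a false improvement is a patient within about 1.3 years below the cut-off at baseline, with absent covered reflexes and age re-evaluated at each visit. One such patient with one absent pair shifts the mean by 0.20 to 0.25 points out of 244. The by-patient NIS listing in SAP 4.4.2.1 would allow an abrupt drop to be looked into. The endpoint is descriptive, and the primary TTR analysis and sample size do not depend on it.

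This rests on two assumptions that the documents neither confirm nor contradict: that the manuals carry the examiner's grading rule, and that one rule is used at all visits.

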7.1.2. Norfolk Quality of Life-Diabetic Neuropathy (Norfolk QoL-DN)

Norfolk QoL-DN is a tool for assessing patients' perception of the effects of diabetes and diabetic neuropathy. There are 35 questions divided into 5 domains. The range of possible total scores is -4 to 136.

Part I: Symptoms

Items 1-7 (Part I) are a simple inventory of symptoms of neuropathy. The presence of the symptom is checked in whichever box applies, and an absence of a symptom is checked under "none." Positive responses are scored as 1; and negative responses, as 0.

Part II: Activities of Daily Life

Items 8-35 (Part II) pertain to Activities of Daily Life, and most of these are scaled on a 5-point Likert scale ranging from 0 ("Not a problem") to 4 ("Severe problem"). However, Questions 31 and 32 are scored differently. In Question 31, "Good," the middle item, is scored as 0. "Very Good" is scored as -1, "Excellent" is scored as -2. "Fair" is scored as 1, and "Poor" is scored as 2. In Question 32, "About the Same," the middle item, is scored as 0. "Somewhat better" is scored as -1, "Much better" is scored as -2. "Somewhat worse" is scored as 1 and "Much worse" is scored as 2.

Subscales and Scoring Algorithm

The Total QoL and 5 domains should be summed as follows:

- Total QoL (35 items) $\Sigma(1-7, 8-35)$
- Physical Functioning/Large Fiber (15 items) $\Sigma(8, 11, 13-15, 24, 27-35)$
- Activities of Daily Living (ADLs) (5 items) $\Sigma(12, 22, 23, 25, 26)$
- Symptoms (8 items) $\Sigma(1-7, 9)$
- Small Fiber (4 items) $\Sigma(10, 16, 17, 18)$
- Autonomic (3 items) $\Sigma(19, 20, 21)$

If at least 50% of the items are non-missing, domain scores are calculated as the average scores of non-missing included items multiplied by the number of items in the domain, rounded to the nearest integer. A domain score is missing if more than 50% of the included items are missing.

If the scores for all 5 domains are non-missing, then Total QoL is the sum of scores of the 5 domains; however, if at least 1 of the domains is missing and at least 50% of the items (18 items) are non-missing, then Total QoL is calculated as 35 times the mean of the non-missing items, rounded to the nearest integer. Otherwise, Total QoL is deemed as missing.

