6.2.3. Norfolk Quality of Life - Diabetic Neuropathy Questionnaire

Quality of life will be assessed through the Norfolk Quality of Life-Diabetic Neuropathy (QOL-DN) questionnaire. The Norfolk QoL-DN scale is a patient-reported assessment that evaluates the subjective experience of neuropathy in the following domains: physical functioning/large fiber neuropathy, activities of daily living, symptoms, small fiber neuropathy, and autonomic neuropathy. The version of the Norfolk QoL-DN that was used in the trial had a total score range from -4 to 136, with higher scores representing greater impairment. The questionnaire will be administered at the time points specified in [Table 1](#).

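### Norfolk QoL-DN proration (SAP 7.1.2) averages Questions 31 and 32, scored -2 to +2, with items scored 0 to 4, so scores with blank items carry avoidable error and can leave the instrument's range

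*SAP*

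**What the plan says.** SAP 7.1.2 scores most Part II items (8-35) from 0 to 4 and then makes an exception: "However, Questions 31 and 32 are scored differently". For these two questions the middle response is 0 and the extremes are -2 and +2. Both belong to the Physical Functioning/Large Fiber domain (items 8, 11, 13-15, 24 and 27-35).

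If at least half of a domain's items are answered, "domain scores are calculated as the average scores of non-missing included items multiplied by the number of items in the domain", rounded to an integer. The total is the sum of the five domains. If a domain is missing but at least 18 items are answered, "Total QoL is calculated as 35 times the mean of the non-missing items", again rounded. Neither rule rescales Questions 31 and 32 or caps the result.

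The same section says: "The range of possible total scores is -4 to 136". Protocol 6.2.3 agrees: "total score range from -4 to 136, with higher scores representing greater impairment".

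SAP 3.10.1 carries the partially imputed score into every analysis and replaces a missing Month 12 score with the Month 6 value. SAP 7.1 treats a single-response question with several answers as missing, which is a further source of blanks.

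**The concern.** Multiplying a mean of answered items by the number of items gives every blank item that mean. This is reasonable when all items share a scale. Here, a blank Question 31 or 32 receives a value driven by 13 items whose midpoint is 2, although its own midpoint is 0. Conversely, a blank 0-4 item is filled with a mean that includes two answers on the shifted scale. The fallback total has the same defect.

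Norfolk QoL-DN change at 12 months is a secondary endpoint, and 20 patients are planned. A mis-prorated score enters the change from baseline directly. If it occurs at Month 6 and Month 12 is missing, last observation carried forward uses it twice.

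**Working it through.** **Reproducing the stated range.** Questions 31 and 32 supply the only negative scores: 2 x (-2) = -4. The maximum is 26 x 4 + 2 x 2 + 7b = 108 + 7b, where b is the most that one symptom item (1-7) can score. The SAP does not state b. Values of 1, 2, 3 and 4 give 115, 122, 129 and 136, so only b = 4 reproduces 136. It is therefore inferred. The text, "Positive responses are scored as 1; and negative responses, as 0", could also be read as b = 1.

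**Physical Functioning domain.** The true range is 2 x (-2) = -4 to 13 x 4 + 2 x 2 = 56. At least 8 of the 15 items must be answered.
- Questions 31 and 32 blank, the other 13 at 4: 52/13 x 15 = 60.
- One of the two blank, the rest at maximum: 54/14 x 15 = 57.9, rounded to 58.
- Questions 31 and 32 both -2, other answered items 0: one blank gives -4/14 x 15 = -4.29 (rounds to -4, in range), two give -4/13 x 15 = -4.62 (rounds to -5), and seven give -4/8 x 15 = -7.5.

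**Fallback total** (18 or more of 35 answered).
- Eighteen items all at 4: 4 x 35 = 140.
- Questions 31 and 32 both -2 plus sixteen zeros: -4/18 x 35 = -7.8, rounded to -8.

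Both fallback extremes hold for b = 1 and for b = 4. Summing the five domains, the maximum is 60 + 20 + 32 + 16 + 12 = 140 if b = 4. If b = 1 it is 60 + 20 + 14 + 16 + 12 = 122.

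**Error for patients away from the extremes.** Let m be the mean of the 0-4 function items and q the mean of the true answers to Questions 31 and 32. Errors are before rounding.
- Both questions blank: 15m - (13m + 2q) = 2(m - q). For assumed m of 0.5 to 2.5 and q of -2 to 2 this runs from -3 to +9. It is zero only when q = m.
- k of the 0-4 items blank, and those items also averaging m: -2k(m - q)/(15 - k). With m - q = 2, one blank gives -4/14 = -0.29 and seven give -28/8 = -3.5.

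**Example.** Let m = 2, Question 31 = +1 and Question 32 = -1. The true score is 26 + 1 - 1 = 26. With both blank, the rule gives 30 (+4). With Question 32 alone blank, it gives 27/14 x 15 = 28.9, rounded to 29 (+3). One such patient moves the mean by 3/20 = 0.15 to 4/16 = 0.25 points for 16 to 20 patients.

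**Effect of the remedies.** Filling blank 0-4 items from answered 0-4 items and limiting imputed Questions 31 and 32 to -2 to +2 turns 60 into 52 + 2 + 2 = 56, and -7.5 into -4. It does not change the example, where the imputed values (2, or 27/14 = 1.93) already lie inside the limit.

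A common-scale alternative adds 2 to both questions, prorates, then subtracts 4. In the example it gives 30 - 4 = 26 with both blank, and 29/14 x 15 - 4 = 27.1 with Question 32 blank. With both blank its error is 2(m - q) - 4, so m - q = 2 is exactly the case where it is error-free. It beats the raw rule only when m - q exceeds 1. For example, with m = 2, Question 31 = 2 and Question 32 = 1, the true score is 29. The raw rule gives 30 (+1) and the common-scale rule 26 (-3).

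**The case against.** The strongest reply is that little depends on this. Out-of-range scores need near-floor or near-ceiling answers. A domain score of 60 needs all 13 function items at 4, yet Protocol 4.2 excludes PND IV and Protocol 4.1 requires Karnofsky status of at least 70. The low breach needs the best answers to both questions, zeros on everything else answered, and at least two further blanks in the domain (or use of the fallback), in patients enrolled for progressing neuropathy. SAP 3.2 makes all non-primary summaries descriptive. All of this stands and limits the point, but it does not justify averaging across two scales.

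A reader might infer that the rule works against the drug, because a patient who feels better scores negatively on Question 32 and a blank there removes that credit. The documents do not support a net direction. The error changes sign with m - q, blanks at baseline act on the change in the opposite direction to blanks at Month 12, and blank 0-4 items usually lower the score. A reader might also infer that the stated range is wrong. It is not: it follows from the scoring with b = 4. The fault lies in the proration.

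The last objection is comparability. The documents do not say whether 7.1.2 follows the instrument's own scoring or the pivotal Phase 3 study's, and SAP 5 relies on that study's Norfolk results to justify last observation carried forward. This is a fair reason to keep the raw rule as a sensitivity analysis.

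**Conclusion.** The defect is real and small. As written, the rule can give a domain score of -7.5 or 60 against a true -4 to 56, and a fallback total of -7.8 or 140 against the SAP's own -4 to 136. Neither document corrects this.

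The range breaches follow from the SAP's text. Two qualifications apply: a total above 136 by summing domains needs symptom items scored 0-4, and the sizes away from the extremes rest on assumed answers. No item-level data or rate of blank items is given, so the effect on the Month 12 mean cannot be estimated beyond about 0.15 to 0.25 points per patient in the example. No test or decision depends on it.

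**What to change.** In SAP 7.1.2:

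1. Fill blank 0-4 items from the answered 0-4 items only.
2. Limit any value imputed for Question 31 or 32 to -2 to +2. Moving an imputed value to the nearest end of its item's range cannot take it further from the true answer. When only these two questions are blank, the same holds for the domain score before rounding. If other items are blank too, errors may offset, so the guarantee is per item.
3. Apply both rules to the 35-item fallback total.
4. State the scoring range of items 1-7. If they score 0 or 1, the Symptoms domain mixes scales too: item 9 at 4, three symptoms at 1 and four blank give 7/4 x 8 = 14 against a true maximum of 11. Items 1-7 would then need separate filling there and in the fallback.
5. Report the raw rule as a sensitivity analysis.

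The limit restores the range without claiming to recover the true answer. Common-scale proration is an acceptable alternative, but it assumes the same relative position on every item, which the documents do not support.

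The cost is a few lines of SAP text and programming. Complete questionnaires keep their scores. A few prorated scores may differ from the pivotal study's if it used the raw rule.

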7.1.3. Rasch-Built Overall Disability Scale (R-ODS)

The R-ODS consists of 24 items scored on a scale of 0 (unable to perform), 1 (able to perform, but with difficulty) or 2 (able to perform without difficulty). A total score will be calculated as the average of all non-missing items multiplied by 24 if at least 90% of the items are non-missing. The total score will be deemed as missing if more than 10% of the items (3 or more items) are missing.

7.1.4. Composite Autonomic Symptom Score-31 (COMPASS-31)

The COMPASS-31 questionnaire comprises 6 domains: Orthostatic intolerance, Vasomotor, Secretomotor, Gastrointestinal, Bladder, and Pupillomotor. Within each domain, individual questions are scored as follows: Simple yes or no questions are scored as 0 points for no and 1 point for yes. Questions about a specific site of symptoms or symptoms under specific circumstances are scored as 0 if not present and as 1 if present for each site or circumstance. All questions regarding the frequency of symptoms are scored as 0 points for rarely or never, 1 point for occasionally or sometimes, 2 points for frequently or “a lot of the time,” and 3 points for almost always or constantly. All questions regarding the severity of symptoms are scored as 1 point for mild, 2 points for moderate, and 3 points for severe. Questions assessing the time course of a symptom are scored 0 points for responses such as “gotten somewhat better,” “gotten much better,” “completely gone,” and “I have not had any of these symptoms,” 1 point for “stayed about the same,” 2 points for “gotten somewhat worse,” and 3 points for “gotten much worse.” The scores for changes in bodily functions depend on the individual question asked. For example, “I get full a lot more quickly than I used to when eating a meal” is scored 2 points and “I get full a lot less quickly than I used to” is scored 0 points, while the answer “I sweat much more than I used to” is given 1 point and “I sweat much less than I used to” is scored 2 points.

The overall scoring proceeds as follows:

- Sum the numerical values associated with responses in each domain
- Apply the following weighting factors to the domain sums:
 - Orthostatic intolerance, 4.0
 - Vasomotor, 0.83333333
 - Secretomotor, 2.1428571
 - Gastrointestinal, 0.8928571
 - Bladder, 1.1111111
 - Pupillomotor, 0.3333333
- Sum the weighted domain scores to obtain a total weighted score (maximum of 100)

Within each domain, there are “gatekeeper” questions. For example, consider questions 5-7:

5. In the past year, have you ever noticed color changes in your skin, such as red, white, or purple?

- 1 Yes
- 2 No (if you marked No, please skip to question 8)

6. What parts of your body are affected by these color changes? (Check all that apply)

- 1 Hands
- 2 Feet

7. Are these changes in your skin color:

- | | |
|---|-------------------------|
| 1 | Getting much worse |
| 2 | Getting somewhat worse |
| 3 | Staying about the same |
| 4 | Getting somewhat better |
| 5 | Getting much better |
| 6 | Completely gone |

Answering “No” to question 5 obviates questions 6-7. Similarly, answering “Yes” to question 5 causes the responses to questions 6-7 to be summed in the resulting overall score. A failure to answer question 5 would render responses to questions 6-7 problematic. Question 5 is the gatekeeper question and question 6-7 will be referred as subsequent questions.

The full list of gatekeeper questions is:

- Question 1: Gatekeeper to questions, 2, 3, 4
- Question 5: Gatekeeper to question 6, 7
- Question 16: Gatekeeper to questions 17, 18, 19
- Question 20: Gatekeeper to questions, 21, 22, 23
- Question 27: Gatekeeper to question 28
- Question 29: Gatekeeper to question 30

A domain score will be deemed as missing if:

1. Answering “No” or “Never” to gatekeeper question but non-missing responses to any of the subsequent questions.
2. Answering “Yes” to gatekeeper question but 1 or more missing responses to subsequent questions, with the exception of missing responses to question 6 which will be scored as 0.
3. Missing response to gatekeeper question and 1 or more missing responses to subsequent questions.
4. Multiple responses to the same question within a domain, with the exception of question 6 that says, “check all.”
5. Missing response to a question within a domain that is not part of a gatekeeper/ subsequent question set. These questions are: 8, 9, 10, 11, 12, 13, 14, 15, 24, 25, 26, 31. The exception is when both questions 9 & 10 are answered as “No” and question 11 is missing, the score will be 0.

When a gatekeeper question is missing response, but all subsequent questions are non-missing, the gatekeeper question will be imputed as “Yes” or the max impairment (example: “Constantly” for questions 27 and 29). For questions 9, 10, and 11, if both questions 9 and 10 are missing responses and the response to question 11 is “1,” question 9 & 10 will be imputed as “No.” For all other responses, question 9 & 10 will be imputed as “Yes.”

For each patient, if ≤ 2 domain scores are missing, the total score will be calculated by imputing the missing domain score by the average domain score using data from any of the patients who

had non-missing score for that domain at the time point. If more than 2 domain scores are missing, the total score will be deemed as missing.

The full text of the COMPASS-31 is below.

1. In the past year, have you ever felt faint, dizzy, “goofy”, or had difficulty thinking soon after standing up from a sitting or lying position?
 - 1 Yes
 - 2 No (if you marked No, please skip to question 5)
2. When standing up, how frequently do you get these feelings or symptoms?
 - 1 Rarely
 - 2 Occasionally
 - 3 Frequently
 - 4 Almost Always
3. How would you rate the severity of these feelings or symptoms?
 - 1 Mild
 - 2 Moderate
 - 3 Severe
4. In the past year, have these feelings or symptoms that you have experienced:
 - 1 Gotten much worse
 - 2 Gotten somewhat worse
 - 3 Stayed about the same
 - 4 Gotten somewhat better
 - 5 Gotten much better
 - 6 Completely gone
5. In the past year, have you ever noticed color changes in your skin, such as red, white, or purple?
 - 1 Yes
 - 2 No (if you marked No, please skip to question 8)
6. What parts of your body are affected by these color changes? (Check all that apply)
 - 1 Hands
 - 2 Feet
7. Are these changes in your skin color:
 - 1 Getting much worse
 - 2 Getting somewhat worse
 - 3 Staying about the same
 - 4 Getting somewhat better
 - 5 Getting much better
 - 6 Completely gone
8. In the past 5 years, what changes, if any, have occurred in your general body sweating?
 - 1 I sweat much more than I used to
 - 2 I sweat somewhat more than I used to
 - 3 I haven’t noticed any changes in my sweating
 - 4 I sweat somewhat less than I used to
 - 5 I sweat much less than I used to
9. Do your eyes feel excessively dry?
 - 1 Yes
 - 2 No

10. Does your mouth feel excessively dry?

- 1 Yes
- 2 No

11. For the symptom of dry eyes or dry mouth that you have had for the longest period of time, is this symptom:

- 1 I have not had any of these symptoms
- 2 Getting much worse
- 3 Getting somewhat worse
- 4 Staying about the same
- 5 Getting somewhat better
- 6 Getting much better
- 7 Completely gone

12. In the past year, have you noticed any changes in how quickly you get full when eating a meal?

- 1 I get full a lot more quickly now than I used to
- 2 I get full more quickly now than I used to
- 3 I haven't noticed any change
- 4 I get full less quickly now than I used to
- 5 I get full a lot less quickly now than I used to

13. In the past year, have you felt excessively full or persistently full (bloated feeling) after a meal?

- 1 Never
- 2 Sometimes
- 3 A lot of the time

14. In the past year, have you vomited after a meal?

- 1 Never
- 2 Sometimes
- 3 A lot of the time

15. In the past year, have you had a cramping or colicky abdominal pain?

- 1 Never
- 2 Sometimes
- 3 A lot of the time

16. In the past year, have you had any bouts of diarrhea?

- 1 Yes
- 2 No (if you marked No, please skip to question 20)

17. How frequently does this occur?

- 1 Rarely
- 2 Occasionally
- 3 Frequently _____ times per month
- 4 Constantly

18. How severe are these bouts of diarrhea?

- 1 Mild
- 2 Moderate
- 3 Severe

19. Are your bouts of diarrhea getting:

- 1 Much worse
- 2 Somewhat worse
- 3 Staying the same
- 4 Somewhat better
- 5 Much better
- 6 Completely gone

20. In the past year, have you been constipated?

- 1 Yes
- 2 No (if you marked No, please skip to question 24)

21. How frequently are you constipated?

- 1 Rarely
- 2 Occasionally
- 3 Frequently _____ times per month
- 4 Constantly

22. How severe are these episodes of constipation?

- 1 Mild
- 2 Moderate
- 3 Severe

23. Is your constipation getting:

- 1 Much worse
- 2 Somewhat worse
- 3 Staying the same
- 4 Somewhat better
- 5 Much better
- 6 Completely gone

24. In the past year, have you ever lost control of your bladder function?

- 1 Never
- 2 Occasionally
- 3 Frequently _____ times per month
- 4 Constantly

25. In the past year, have you had difficulty passing urine?

- 1 Never
- 2 Occasionally
- 3 Frequently _____ times per month
- 4 Constantly

26. In the past year, have you had trouble completely emptying your bladder?

- 1 Never
- 2 Occasionally
- 3 Frequently _____ times per month
- 4 Constantly

27. In the past year, without sunglasses or tinted glasses, has bright light bothered your eyes?

- 1 Never (if you marked Never, please skip to question 29)
- 2 Occasionally
- 3 Frequently
- 4 Constantly

28. How severe is this sensitivity to bright light?

- 1 Mild
- 2 Moderate
- 3 Severe

29. In the past year, have you had trouble focusing your eyes?

- 1 Never (if you marked Never, please skip to question 31)
- 2 Occasionally
- 3 Frequently
- 4 Constantly

30. How severe is this focusing problem?

- 1 Mild
- 2 Moderate
- 3 Severe

31. Is the most troublesome symptom with your eyes (ie, sensitivity to bright light or trouble focusing) getting:

- 1 I have not had any of these symptoms
- 2 Much worse
- 3 Somewhat worse
- 4 Staying about the same
- 5 Somewhat better
- 6 Much better
- 7 Completely gone

